Table 3	Exploratory Efficacy Objectives and EndpointsError! Bookmark not defined
Table 4	Minimum detectable difference between each IXT-m200 group versus the placebo group
Table 5	Analysis Populations9

Version history

Table 1 documents the changes to the SAP through all versions. Details regarding protocol changes that resulted in changes to the SAP can be found in the respective protocol amendment.

 Table 1
 SAP Version History Summary

SAP Version Approval Date	Rationale	Changes to SAP
1 24MAY2021	Original version	Not Applicable
2 01DEC2021		Changes to endpoints Addition of pseudo-SAS code for spaghetti plot
3 21MAR2023	The focus of the trial has shifted from a potentially pivotal trial to a purely Phase II, information gathering trial.	Change layout of SAP Incorporate suggestions from internal and FDA discussions, regarding objectives/endpoints and analyses. Addition of pseudo-R code for plots
4 01JUN2023	Fixing errors in endpoints	Fixed error in exploratory endpoint Updated table of contents
5 14JUL2023	Changes to protocol	Updated order of endpoints Updated study design
01MAY2024	Adding pharmacokinetic parameters to the analyses	Added pharmacokinetic endpoints Fixed discrepancy in endpoint regarding imputation of missing data

Abbreviations/Definitions

Abbreviation	Definition
AE	adverse event
ALT	alanine aminotransferase
AST	aspartate aminotransferase
app	application
BMI	body mass index
BUN	blood urea nitrogen
CBT	cognitive behavioral therapy
CDFs	cumulative distribution functions
CI	confidence interval
C-SSRS	Columbia Suicide Severity Rating Scale
DSM-V	Diagnostic and Statistical Manual of Mental Disorders, 5 th edition
DSMB	Data and Safety Monitoring Board
ECG	electrocardiogram
eCFR	electronic case report form
HIPPA	Health Insurance Portability and Accountability Act of 1996
ICH	International Council for Harmonisation
IRT	interactive response technology
ITT	intent-to-treat
IV	intravenous
LLOQ	lower limit of detection
MedDRA	Medical Dictionary for Regulatory Activities
METH	methamphetamine
MI	multiple imputation
mITT	modified intent-to-treat
MMRM	mixed model repeated measures
MUD	methamphetamine use disorder
PI	principal investigator
PK	pharmacokinetic

Abbreviation	Definition
PP	per-protocol
PT	preferred term
SAE	serious adverse event
SAP	statistical analysis plan
SD	standard deviation
SOC	system organ class
SPRHK1	SelfReportPHarmacoKinetic1

SAP Approval Signature Page

PROTOCOL TITLE	OUTLAST: A Phase 2 Double-Blind, Randomized, Placebo- Controlled, Multiple-Dose Study to Evaluate the Safety and Efficacy of IXT-m200 in Treatment-Seeking Individuals with Methamphetamine Use Disorder	
SAP Version, Date	V5, 01May2024	
SAP AUTHOR	[name] Director, Biostatistics EMB Statistical Solutions, LLC	
Investigational Product	IXT-m200	
Protocol Number	M200C-2201	
Protocol Version, Date	5 03Feb2023	
Signature Statement By my signature, I indicate I have reviewed this SAP and find its contents to be acceptable.		
Reviewers on behalf of InterveXion Therapeutics, LLC		
Approver Signature	Date	
_	[name], MBA, PhD Chief Operating Officer Sponsor	

1. Introduction

The purpose of this SAP is to describe the analysis variables and statistical procedures that will be used to analyze and report the results of InterveXion's protocol M200C-2201. This study is a Phase 2A study evaluating the safety, efficacy, immunogenicity, and pharmacokinetics (PK) of IXT-m200, a chimeric anti-methamphetamine monoclonal antibody treatment, in treatment-seeking individuals with methamphetamine (METH) use disorder (MUD). This statistical analysis plan (SAP) is based on InterveXion's protocol M200C-2201 version 5, dated February 3, 2023.

The SAP was written in accordance with the recommendations outlined in the International Conference on Harmonization (ICH) E9 Guideline entitled "Guidance for Industry: Statistical Principles for Clinical Trials" and the ICH-E3 Guideline entitled "Guidance for Industry: Structure and Content of Clinical Study Reports".

Some of the analyses detailed here may be more explicit or in some respects different from those stated in the protocol. In case of differences, this SAP supersedes the statistical sections in the protocol.

Most statistical analyses will be performed using SAS® version 9.4 or later, with SAS program code prepared specifically for the project by qualified statisticians and SAS programmers. Other validated programs (e.g., S-Plus, R) may be used for graphs or for specialized analyses.

Changes to the protocol that impact the design, the data collected, or the statistical methods and that occur after the finalization of this SAP may require amendment of the approved SAP. Similarly, changes to the planned analysis variables and/or statistical methods described in the approved SAP may also require amendment of the SAP, so long as the changes were implemented prior to database lock. Changes in planned analyses that are decided after database lock will be documented in the clinical study report (CSR).

The formats for the tables, listings, and figures described in this SAP are provided in a companion document. Changes to the formats of these reports that are decided after the finalization of the SAP will not require an amendment. In addition, any additional supportive or exploratory analyses requested after SAP approval will not require amendment of the SAP and will instead be described in the CSR.

Please see the study protocol for details about the study design, procedures, and schedule of assessments and see the electronic case report form (eCRF) for details about variables collected and their possible values.

1.1. Objectives, Endpoints, and Estimands

The following Table 2 lists the primary and secondary efficacy objectives of the study, along with the endpoints that will be measured, the clinical question to be addressed, as well as the estimand. An estimand is defined in the ICH E9(R1) guidance as "...the target of estimation to address the scientific question of interest posed by the trial objective."

Table 2 Primary and Secondary Efficacy Objectives, Endpoints and Estimands

Primary		
Objective: To evaluate the efficacy of IXT-m200 in preventing or	Endpoints: Percent of 20 weeks abstinent from stimulants following a 4-week grace period (between Week 5 and Week 25) as measured by saliva screens.	
reducing relapse to stimulant use.	Clinical Question: Does adding IXT-m200 to standardized cognitive behavioral therapy (CBT) program improve the percent of 20 weeks abstinent from stimulants following a 4-week grace period, relative to the CBT program alone, in treatment-seeking participants, regardless of IXT-m200 interruption or discontinuation, for any reason?	
	Estimand: The difference in group means between the IXT-m200 and placebo groups for the percent of 20 weeks abstinent from stimulants following a 4-week grace period as measured by saliva screens in treatment-seeking individuals with MUD. All observations will be used, regardless of whether a participant discontinued treatment early. All missing values will be imputed assuming the participant is not abstinent.	
	Secondary	
Objective: To evaluate the efficacy of IXT-m200 in improving	Endpoints: Change from screening in participant-rated quality of life as measured by the Treatment Effectiveness Assessment (TEA) at Week 13, 25, and Week 33.	
participant-rated quality of life.	Clinical Question: Does adding IXT-m200 to standardized CBT program improve the change from screening in participant-rated quality of life relative to the CBT program alone in treatment-seeking participants regardless of IXT-m200 interruption or discontinuation, for any reason?	
	Estimand: The difference in group medians for the change from screening in participant-rated quality of life at Week 13, 25, and 33 between the IXT-m200 and placebo groups. All observations will be used, regardless of whether a participant discontinued treatment early. Missing values will not be imputed.	
Objective: To evaluate the efficacy of IXT-m200 in increasing the number of participants	Endpoints: Responders at Week 25 as measured by the DSM-5 criteria. A responder is a participant who meets the definition of early remission, i.e., ≥3 months and <12 months without meeting DSM-5 criteria, while disregarding the result for craving.	
achieving early remission.	Clinical Question: Does adding IXT-m200 to standardized CBT program improve the proportion of participants achieving early remission, relative to the CBT program alone in treatment-seeking participants regardless of IXT-m200 interruption or discontinuation, for any reason?	
	Estimand: The difference in the proportion of responders between the IXT-m200 and placebo groups, where a responder is a participant who meets the definition of early remission, i.e., ≥3 months and <12 months without meeting DSM-5 criteria, other than craving. All observations will be used, regardless of whether a participant discontinued treatment early. All missing values will be imputed assuming the participant has not achieved early remission.	
Objective: To evaluate the efficacy of IXT-m200 in improving	Endpoints: Difference between groups in Clinical Global Impression of Change (CGIC) at Week 13, 25, and Week 33.	

clinician-rated response to treatment.	Clinical Question: Does adding IXT-m200 to standardized CBT program improve CGIC at Week 13, 25, and Week 33, relative to the CBT program alone in treatment-seeking participants regardless of IXT-m200 interruption or discontinuation, for any reason? Estimand: The difference in CGIC at Week 13, 25, and Week 33, between the IXT-m200 and placebo groups in treatment-seeking individuals with MUD. All observations will be used, regardless of whether a participant discontinued treatment early. Missing values will not be imputed.
Objective: To evaluate the efficacy of IXT-m200 in improving patient-rated response to treatment.	Endpoints: Difference between groups in Patient Global Impression of Change (PGIC) at Week 13, 25, and Week 33. Clinical Question: Does adding IXT-m200 to standardized CBT program improve PGIC at Week 13, 25, and Week 33, relative to the CBT program alone in treatment-seeking participants regardless of IXT-m200 interruption or discontinuation, for any reason? Estimand: The difference in CGIC at Week 13, 25, and Week 33, between the IXT-m200 and placebo groups in treatment-seeking individuals with MUD. All observations will be used, regardless of whether a participant discontinued treatment early. Missing values will not be imputed.

Table 3 Exploratory Efficacy Objectives and Endpoints

Exploratory Objectives	Endpoints
To evaluate the efficacy of IXT-m200 in increasing the number of participants achieving early remission.	Responders at Week 33 as measured by DSM-5 criteria. A responder is a participant who meets the definition of early remission, i.e., ≥3 months and <12 months without meeting DSM-5 criteria while disregarding the result for craving.
To evaluate the efficacy of IXT-m200 in reducing the number of adverse outcomes from the Adverse Outcomes Assessment.	The difference between groups in the number of adverse outcomes reported at Week 13, 25, and Week 33.
To evaluate the efficacy of IXT-m200 in preventing or reducing relapse to stimulant use, as measured by self-report surveys.	Percent of days abstinent from stimulants following a 4-week grace period (between Week 5 and Week 25) as measured by self-report.
To evaluate the efficacy of IXT-m200 in improving the length of sustained abstinence.	Number of sequential weeks of abstinence from the end of treatment visit (Week 25), defined as four weeks after the final planned dose of study drug (at Week 21), as measured by saliva screens.
To evaluate the efficacy of IXT-m200 in improving post-treatment abstinence.	Point prevalence abstinence (last 7 days) as measured by saliva screens at Week 25, Week 29, and Week 33.
To evaluate the efficacy of	Complete abstinence during the last month of study drug treatment (between Week 21 and Week 25), as measured by saliva screens.

IXT-m200 in improving the proportion of participants achieving stimulant abstinence. To evaluate the efficacy of IXT-m200 in reducing the frequency of METH use over time, as measured by self-report. To evaluate the efficacy of IXT-m200 in preventing or reducing relapse to stimulant use, as measured by self-report.	Difference between groups in the trend over time in the number of use days per week, as measured by self-report for Weeks 5 through 25. Proportion of participants with n or fewer use days between Week 5 and Week 25 measured by self-report.
To evaluate the efficacy of IXT-m200 in preventing or reducing relapse to stimulant use, as measured by saliva screens.	Proportion of participants with n or fewer use days between Week 5 and Week 25 measured by saliva screens.

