9.4.2 ANALYSIS OF THE PRIMARY EFFICACY ENDPOINT(S)

The primary efficacy endpoint is percent of 20 weeks abstinent from stimulants based on saliva screens and by self-report via smartphone app during a 20-week period between Week 5 and Week 25, after a four-week grace period during which relapses may occur. A combination of self-report and saliva screens data and concordance will be used to score each day of the study within these time frames. The primary efficacy endpoint analysis will use the ITT population.

Participants self-report stimulant use on a daily basis; a saliva screen is taken twice a week at two random timepoints. Data that contribute to the primary endpoint will be collected from the day after a participant's Week 5 visit through the next 20 weeks. The SAP will detail the visit windows.

A modified combined self-report and pharmacokinetic-1 (SRPHK1) algorithm⁸ will be used to derive if a day is a "use day" or an "abstinent day". Briefly the rules of the algorithm (as listed in Somoza et al., 2008 with minor modifications) are:

1. Always label self-reported use days as use days.
2. Label any day covered by a positive saliva screen as a use day. However, if that day is a self-reported no-use day and one of the one or two previous days was self-reported as a use day, assign the saliva-based use to the self-reported use day. If self-report is missing for the day prior to the positive saliva sample, the day will be considered a use day.
3. Label as missing any self-reported no-use days not followed by a saliva sample within 7 days. Also label as missing any day having a missing self-report and no saliva-based indication of use or no use.
4. Treat all other self-reported no-use days (temporarily) as "unknown".
5. Treat "unknown" days as described below:
 - a. Calculate the "concordance rate" as follows:
 - (1) determine the number of instances in which a day has been assigned a saliva screen status of use but the participant reports no use;
 - (2) divide this number by the total number of saliva samples;
 - (3) subtract the resulting fraction from 1.
 - b. If the concordance rate is ≥ 0.7 (i.e., if we can trust that the participant tells the truth in his or her self-report), label all remaining "unknown" days as no-use days; otherwise label all remaining "unknown" days as missing.
6. Weeks with missing values for every day will be imputed as a non-abstinent week.

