A visit week with no use days is an abstinent week and a visit week with any use day is a non-abstinent week. For each participant, the percent weeks abstinent is the number of weeks (observed or imputed) divided by the weeks in the period of interest (i.e., 20 weeks for the primary endpoint).

The primary efficacy analysis is based on a test of the difference between each IXT-m200 dose group and the placebo group in percent weeks abstinent, as estimated using an analysis of covariance (ANCOVA). The dependent variable in the model is percent weeks abstinent; the independent variables in the model will be treatment group assignment and stratification level of past-month METH use at screening.

Adjusted means and standard errors for each treatment group and the estimated difference between the groups and associated 95% confidence intervals and two-sided p-values will be reported.

Sensitivity analyses will be described in the SAP and may explore the impact of missing data and standard-based imputation with control-based MI.

Details of the primary and sensitivity analyses, including imputation models, will be described in the SAP.

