4.6.1. Main analytical approach

The primary efficacy analysis will use the ITT population and is based on a test of the mean difference between each IXT-m200 group and the placebo group in percent weeks abstinent, as estimated using an analysis of covariance (ANCOVA). The dependent variable in the model is percent weeks abstinent; the independent variables in the model are the following:

- Treatment group assignment (discrete); and
- Stratification level of past-month METH use at screening (discrete).

[figure not shown]
The data for this primary endpoint will have shown efficacy if the test of mean percent weeks abstinent between Week 5 and Week 25 shows nominal statistically significant benefit in any IXT-m200 group relative to the placebo group.

Adjusted means and standard errors for each treatment group and the estimated difference between the groups and associated 95% confidence intervals and two-sided p-values will be reported. A plot of all saliva screen results for each individual subject throughout the study will be provided. Pseudo-R code for the plot is included in Exhibit 2. The data should be divided into subsets based on the value of the saliva test value for methamphetamine, including 'positive', 'negative', 'missed', 'invalid'. If the result of a saliva screen is not one that is listed, the sponsor should be contacted to receive instruction on how to code the value. If a saliva screen test is missed, that week will be imputed assuming the participant is not abstinent. If a participant withdraws from the study, then all weeks following withdrawal will be assumed as not abstinent. For the *n* subjects, each subject should be assigned a value from 1 to *n* for the purpose of plotting. Participants will be grouped by study treatment. An example plot is available in Exhibit 3.

Exhibit 2 Pseudo-R Code for Saliva Screen Data Plot

```
points(neg placebo$DAY,neg placebo$SUBJIDN,col=rgb(0.2,0.7,0.9,1),pch=17,cex=1)
points(pos placebo$DAY,pos placebo$SUBJIDN,col=rgb(1,0.5,0,1),pch=19,cex=1)
points(miss placebo$DAY,miss placebo$SUBJIDN,col=rgb(1,0.5,0,1),pch=4)
points(inv placebo$DAY,inv placebo$SUBJIDN,col=rgb(1,0.5,0,1),pch=5)
par(mar=c(5,1,4,2))
plot(NA,NA,xlim=c(0,175),ylim=c(0,50),xlab='Study Day',ylab=',main='IXT-M200 Saliva
Screen Results',
    yaxt='n',xaxt='n')
axis(1, at=seq(0, 175, by=7))
axis(2, at=seq(0.50,by=5))
for(i in 0:15){
 polygon(c(14*i+.5,14*i+7.5,14*i+7.5,14*i+.5), c(-5,-
5,75,75),col=rgb(0,0,0,025),border=rgb(0,0,0,025))

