legend(125, 0.2, legend=c('Treatment','Placebo'),
   col = c(rgb(0.2,0.7,0.9,1),rgb(1,0.5,0,1)),lwd=c(1,1))
```

Exhibit 10 Continuous Responder Curve Plot

Continuous Responder Curve

Proportion of participants with *n* or fewer use days between Week 5 and Week 25 Measured by Saliva Screens

The proportion of participants with n or fewer use days between Week 5 and Week 25, where n ranges from 0 to 20 will be summarized. A secondary endpoint is Complete Abstinence during the last 4 weeks. This analysis will expand that to the last 20 weeks and explore a range of use days from 0 (complete abstinence) to 20 (an average of one use day a week).

A "use day" or "abstinent day" will be derived using the following algorithm.

- If a participant has two positive tests, misses two tests, or has one positive and one missing test in a given week, then impute 7 use days for that week.
- If a participant has one positive/missing test and one negative test, then impute 4 use days for that week.
- If a participant tests negative for both tests, then impute 0 use days for that week.

The summary will be descriptive only, presenting the number and percentage of "responders," defined as subjects with n or fewer use days between Week 5 and Week 25. A continuous responder curve will be produced with the number of use days on the horizontal axis and percent of subjects on the vertical axis, with a line for each treatment group. Since the criteria for a responder becomes less strict as n increases, both curves would be expected to be near 0% at n=0, and increase as they move to the right. The graph will allow a visual examination of potential separation between treatment groups.

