4.13. Changes to Protocol-Planned Analyses

• There are no changes to the analyses planned in the protocol.

5. Supporting Documentation

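### The SAP scores the primary endpoint from saliva screens alone, where the protocol combines saliva with self-report; SAP 4.13 declares no change, and no SAP analysis recovers the protocol's endpoint

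*SAP*

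**What the plan says.** **Protocol.** Section 9.4.2 states: "The primary efficacy endpoint is percent of 20 weeks abstinent from stimulants based on saliva screens and by self-report via smartphone app". Six rules, a modified SRPHK1 algorithm, turn the two data streams into a daily use status. Rule 1 is "Always label self-reported use days as use days". Missing data by themselves fail a week only under rule 6: "Weeks with missing values for every day will be imputed as a non-abstinent week". Any use day makes the week non-abstinent, and "the percent weeks abstinent is the number of weeks (observed or imputed) divided by the weeks in the period of interest". That wording, with imputation detail left to the SAP, gives some latitude on missing data.

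**SAP.** Table 2 (Section 1.1) gives the primary endpoint as "Percent of 20 weeks abstinent from stimulants following a 4-week grace period (between Week 5 and Week 25) as measured by saliva screens", and its estimand counts all missing values as not abstinent. Section 4.6.1 adds: "If a saliva screen test is missed, that week will be imputed assuming the participant is not abstinent". That sentence sits in a paragraph about a plot, but it agrees with the estimand.

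**What is declared.** Protocol 9.4.1 expects the SAP to contain any amendments to the protocol's analyses and lets it take precedence. SAP Section 1 claims the same precedence. SAP 4.13 then says: "There are no changes to the analyses planned in the protocol". The SAP version history mentions internal and FDA input on endpoints, a new endpoint order and an imputation correction to an unnamed endpoint. No entry says that self-report left the primary endpoint.

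**The concern.** Two documents give one name to two different outcomes. A reader who relies on 4.13 will take the reported primary result to be the protocol's combined endpoint. It will instead be a saliva-only measure whose value depends on whether screens were completed.

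The trial also sets out to compare ways of measuring response: SAP 4.1 says the plan varies the definition so that the usefulness of each can be judged. The protocol's own combined definition is not among those analysed, so that comparison cannot be made from the planned outputs.

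**Working it through.** **1. The same week under each rule**

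| Week | Protocol 9.4.2 | SAP Table 2 and 4.6.1 |
|---|---|---|
| Use reported, both screens negative | Not abstinent (rule 1) | Abstinent |
| No use reported, one negative and one missed screen | Abstinent, if concordance is at least 0.7 and a sample follows in time | Not abstinent |

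The rules can therefore differ in either direction. Each week scored differently moves a participant by 1/20 = 5 points.

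**2. Other differences that 4.13 does not list**
- CGIC and PGIC: exploratory with ANCOVA (protocol 3 and 9.4.9); secondary with Kruskal-Wallis (SAP 4.7).
- Complete abstinence, Weeks 21 to 25: secondary (protocol 3); exploratory (SAP Table 3), although the text of SAP 4.8 still calls it secondary.
- TEA: MMRM (protocol 9.4.3.3); Kruskal-Wallis (SAP 4.7.1.2).
- Early remission: identity-link binomial model (protocol 9.4.3.1); stratified Mantel-Haenszel (SAP 4.7.1.2).
- Safety: ITT (protocol 9.4.4); Safety population (SAP 4.10).

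**3. Does the protocol endpoint reappear?** SAP 4.6.2 repeats the analysis without imputation, or in the PP set. SAP 4.8 uses self-report only in separate exploratory measures. Nothing combines the streams. Two exploratory endpoints in 4.8 (sequential weeks and point prevalence) take their use days from the primary endpoint's derivation, but the SAP's primary section has no day-level derivation. SRPHK1 survives only in the abbreviation list, misspelled and without its rules.

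**4. Size for one participant.** The plan gives no miss rate and no figure that depends on the scoring rule, so there is none to reproduce. I assume two screens a week (protocol 9.4.2), each missed independently with probability p, and a participant who never uses and truthfully reports no use every day.
- SAP rule: both screens are needed, so the score is (1−p)².
- Protocol rules: a week fails only if all its days are missing under rule 3. If a same-day screen counts, that requires all four screens of that week and the next to be missed, so the score is 1−p⁴. If it does not count, a screen on the week's first day (probability 2/7) cannot help, so the score is 1−p²·[(5/7)p² + (2/7)p].

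| p | SAP | Protocol, same day counts | Protocol, same day does not count |
|---|---|---|---|
| 10% | 81% | 100.0% | 100.0% |
| 20% | 64% | 99.8% | 99.7% |
| 30% | 49% | 99.2% | 98.7% |

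Day-level simulation of the protocol rules gives the same protocol values.

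**5. Size between arms, no true effect.** Take p = 10% on active and 20% on placebo, with a share A of weeks truly abstinent in both arms and misses unrelated to use. The spurious difference is A × (0.81 − 0.64) = A × 0.17:
- A = 20%: 3.4 points
- A = 50%: 8.5 points
- A = 70%: 11.9 points

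Both documents allow dropout of up to 50%. If half the participants leave, evenly over the 20 weeks and equally by arm, 0.5 × 0.5 = 25% of weeks fail under either rule. Multiplying by 0.75 gives 2.6, 6.4 and 8.9 points.

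**6. What the no-imputation repeat does.** If incomplete weeks are dropped, the expected score is about A(1−p)²/(1−p)² = A in each arm, and the difference disappears. The same holds if incomplete weeks are scored on the screens taken, provided any screen in a use week is positive. The repeat does nothing for reported use: someone who reports one use day every week with all screens negative still scores 100%, against 0% under the protocol.

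**The case against.** The strongest reply is that the SAP is allowed to do this and does it openly. It has precedence, it warns that its analyses may differ from the protocol's, and Table 2 states the new endpoint. The measure is not new either: protocol 9.4.9 already lists saliva-only weekly abstinence over the same window as exploratory. The trial is an exploratory Phase 2A with nominal p-values and no multiplicity control. All of this stands. It settles which text governs, but it does not make 4.13 true or supply the missing analysis.

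Nor is the protocol rule a gold standard. If a participant uses, skips screens and reports no use, the protocol can pass a week that the SAP rule fails. That is a fair argument for keeping saliva-only as primary.

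Three stronger readings are tempting, but the documents do not support them:
- *The SAP contradicts itself on missed screens.* For an exploratory use-day count, SAP 4.8 says "If a participant has one positive/missing test and one negative test, then impute 4 use days for that week". A reader might see a conflict with 4.6.1. There is none: it is a separate endpoint, and by the protocol's rule a week with any use day is non-abstinent, so the week fails both ways.
- *The power table is undermined.* SAP Table 4 reproduces: at its 0.78, 0.84 and 0.90 SD, with 40 versus 20, t-test power is 80.0%, 85.5% and 89.8%. It takes the SD as given. SAP 1.2 speaks of the SD of the observed primary endpoint, which points to the endpoint as analysed, and SAP 2.2 says the sample size was not set for power.
- *The change followed sight of interim results.* The documents do not show when the saliva-only choice was made, so no such inference is available.

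**Conclusion.** The concern holds as an undeclared change to the primary endpoint, together with the lack of any analysis of the endpoint the protocol defined. It should be fixed, but it does not invalidate the trial. The textual finding needs no assumptions.

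The sizes are illustrations. They rest on assumed miss rates, independent misses unrelated to use, truthful self-report for the single-participant scores and, for the dropout adjustment, uniform and equal withdrawal. On those terms the spurious arm difference is 3.4 to 11.9 points before dropout and about 2.6 to 8.9 after it. The SAP's own repeat without imputation would largely remove it if incomplete weeks are dropped or scored on the screens taken, so this difference is not wholly unchecked. What remains unchecked is the loss of self-reported use. Its size cannot be worked out, because the documents do not say how long after use a saliva screen stays positive.

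**What to change.** 1. Rewrite SAP 4.13 to list each change from protocol version 5, with its reason and date: the primary endpoint and the five items in step 2 of the working.
2. Keep saliva-only as primary if a justification is stated, and add to SAP 4.6.2: *The percent-weeks-abstinent endpoint of protocol 9.4.2 (rules 1 to 6) will be analysed in the ITT population with the ANCOVA of Section 4.6.1. Missed-screen rates will be reported by arm.* To make this runnable, state which days a positive screen covers (rule 2) and whether a same-day screen meets the 7-day requirement (rule 3).
3. Write out the use-day derivation on which the sequential-weeks and point-prevalence endpoints in SAP 4.8 rely.

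If the database is already locked, record these points in the clinical study report, as SAP Section 1 provides.

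The cost is SAP wording, one derivation, one ANCOVA and one table; both data streams are already collected (protocol 8.1.2 and 8.1.3). The downside is that the two results may disagree, so the SAP must say which one is primary.
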